2.2.2 Randomization and blinding

Patients who meet all eligibility criteria will be enrolled into the study. All patients will be treated with obicetrapib 10 mg. No blinding or randomization is required.

2.2.3 Study drug

Patients will be treated with 10 mg obicetrapib once a day.

Compliance to the study drug regimen will be evaluated by counting unused tablets and capsules. During the Treatment Period, if compliance is not between 80% and 120%, inclusive, the patient will be counselled about the importance of compliance to the regimen. If the limits are exceeded at 2 consecutive visits, a decision will be made by the Investigator and Sponsor as to whether the patient should be withdrawn from the study.

2.2.4 Sample size determination

No formal sample size determination was performed. A total number of 10 to 15 patients is considered sufficient for this proof-of-concept study.

2.3 Study endpoints

2.3.1 Primary pharmacodynamic endpoints

The primary PD endpoint is the change from baseline in levels of apolipoprotein A-I (ApoA-I), apolipoprotein E (ApoE), small high-density lipoprotein (HDL) particles, in both CSF as well as plasma and ABCA1-driven cholesterol efflux in CSF measured at Day 168.

2.3.2 Exploratory pharmacodynamic endpoints

Exploratory analyses may be performed to further investigate the PD of obicetrapib. These may include, but might not be limited to, the following assays at selected time points:

Changes From Baseline Levels in Lipoproteins and Apolipoproteins in Plasma

At Baseline (Visit 2), at Day 84 (Visit 4), and the End of Treatment (Day 168, Visit 6), the following parameters will be measured:

- LDL-C
- Total cholesterol (TC)
- Non-HDL-C
- TG
- ApoB

Changes From Baseline Levels in Lipoproteins and Apolipoproteins in CSF and Plasma

At Screening (Visit 1) or Baseline (Visit 2), at Day 84 (Visit 4), and at the End of Treatment (Day 168, Visit 6), the following parameters will be measured:

- HDL-C
- HDL-ApoE
- Apolipoprotein A-II (ApoA-II)

Note, baseline levels of CSF lipoproteins and apolipoproteins will be determined at Screening (Visit 1) since CSF sampling is required for inclusion. Baseline levels of plasma lipoproteins and apolipoproteins will be determined at Baseline (Visit 2). CSF sampling for CSF lipoproteins and apolipoproteins at Day 84 (Visit 4) is optional.

Change From Baseline Levels in AD Biomarkers in CSF

At Screening (Visit 1), at Day 84 (Visit 4), and at the End of Treatment (Day 168, Visit 6), the following parameters will be measured in the CSF:

- Tau and phosphorylated tau at Thr181 (p-Tau 181)
- Aβ1-42, Aβ1-40, Aβ1-42/Aβ1-40 ratio
- Neurogranin
- Neurofilament light
- Glial fibrillary acidic protein (GFAP)
- sTREM2
- YKL40
- Inflammatory markers (eg, interferon [IFN]-γ, IL-10, IL-12p70, IL-17A, IL-6, TNF-α)

Note, CSF sampling for AD biomarkers in CSF at Day 84 (Visit 4) is optional.

Change From Baseline Levels in AD Biomarkers in Plasma

At Baseline (Visit 2), at Day 84 (Visit 4), and the End of Treatment (Day 168, Visit 6), the following parameters will be measured in the plasma:

- Tau and p-Tau epitopes
- Aβ1-42, Aβ1-40, Aβ1-42/Aβ1-40 ratio
- Neurofilament light

Correlation Between the Change From Baseline Levels in CSF p-Tau 181 and CSF ApoA-I, ApoE, and Cholesterol Efflux Capacity

At Screening (Visit 1) and at the End of Treatment (Day 168, Visit 6), p-Tau 181, ApoA-I, ApoE, and cholesterol efflux capacity will be measured in the CSF.

Change From Baseline Levels in 24-Hydroxycholesterol and 27-Hydroxycholesterol in CSF and Plasma

At Baseline (Visit 2), Day 84 (Visit 4), and the End of Treatment (Day 168, Visit 6), 24 hydroxycholesterol and 27 hydroxycholesterol will be measured in the CSF and plasma samples.

Note, CSF sampling for 24-hydroxycholesterol, 27-hydroxycholesterol, desmosterol, and lathosterol in CSF at Day 84 (Visit 4) is optional.

2.3.3 Exploratory cognition endpoints

Disease Progression Measured With the Cognitive-Functional Composite

At Baseline (Visit 2) and the End of Treatment (Day 168, Visit 6), the CFC test will be administered to allow tracking of disease progression.

Mini-Mental State Examination

At Screening (Visit 1), Baseline (Visit 2), Day 84 (Visit 4), and the End of Treatment (Day 168, Visit 6), the MMSE will be administered.

2.3.4 Exploratory pharmacokinetic endpoints

Mean Plasma Levels of Obicetrapib at Steady State in CSF and Plasma

At Screening objcetrapib concentrations will be measured in the CSF. At Day 1 (Visit 2) objcetrapib concentrations will be measured in plasma. At Day 84 (Visit 4) and the End of Treatment (Day 168, Visit 6), objcetrapib concentrations will be measured in the CSF and plasma samples.

3. Statistical methodology

3.1 General considerations

3.1.1 Analysis day

Analysis day will be calculated from the date of first dose of study drug. The day of the first dose of study drug will be Day 1, and the day immediately before Day 1 will be Day -1. Day 0 will be seen as Baseline.

3.1.2 Definition baseline

Unless otherwise stated, Baseline will be defined as the last measurement prior to the first dose of study drug.

3.1.3 Summary statistics

Categorical data will generally be summarized with counts and percentages of participants. The denominator used for the percentage calculation will be clearly defined. Continuous data will generally be summarized with descriptive statistics including n (number of non-missing values), mean, median, standard deviation, minimum, and maximum.

3.1.4 Handling of dropouts and missing data

Date Values

In cases of incomplete dates (e.g. AE, concomitant medication, and medical history start and/or stop dates), the missing component(s) will be assumed as the most conservative value possible. For example, if the start date is incomplete, the first day of the month will be imputed for the missing day and January will be imputed for the missing month. If a stop date is incomplete, the last day of the month will be imputed for the missing day and December will be imputed for the missing month. Incomplete start and stop dates will be listed as collected without imputation.

Date imputation will only be used for computational purposes such as treatment-emergent status. Actual data values, as they appear in the original CRFs, will be presented within the data listings.

Non-Date Values

For the analyses of primary, secondary and cognitive efficacy endpoints, no imputation will be made for missing values. Safety data will be used according to availability, with no imputation for missing data.

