8 SAFETY ASSESSMENTS

Adverse Events

An AE is defined as any untoward medical occurrence in a clinical investigation patient administered a pharmaceutical product, which does not necessarily have a causal relationship with this treatment. An AE can therefore be any unfavorable and/or unintended sign (including an abnormal laboratory finding), symptom, or disease temporally associated with the use of an investigational medicinal product, whether or not related to the investigational medicinal product. All AEs, including observed or volunteered problems, complaints, or symptoms, are to be recorded on the appropriate eCRF.

AEs, which include clinical laboratory test variables, will be monitored and documented from the time of first dose of study drug until the end of the study. Patients or their study partner should be instructed to report any AE that they experience to the Investigator, whether or not they think the event is due to study drug. Beginning at the date of the first dose of study drug, Investigators should make an assessment for AEs at each visit and record the event on the appropriate AE eCRF.

Wherever possible, a specific disease or syndrome rather than individual associated signs and symptoms should be identified by the Investigator and recorded on the eCRF. However, if an observed or reported sign or symptom is not considered a component of a specific disease or syndrome by the Investigator, it should be recorded as a separate AE on the eCRF. Additionally, the condition that led to a medical or surgical procedure (eg, surgery, endoscopy, tooth extraction, or transfusion) should be recorded as an AE, not the procedure itself.

Any medical condition already present at the date of the first dose of study drug should be recorded as medical history and not be reported as an AE unless the medical condition or signs or symptoms present at baseline change in severity, frequency, or seriousness at any time during the study. In this case, it should be reported as an AE.

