10.1.1 Data Handling

All handling of personal data will comply with the EU General Data Protection Regulation and the Dutch Act on Implementation of the General Data Protection Regulation. If an external organization will process data on behalf of the sponsor, a contractual procedure will be signed between the sponsor and the external organization to ensure compliance with the above-mentioned legislation.

Data will be recorded at the site on eCRFs and reviewed by the monitor during monitoring visits. The monitors will verify data recorded in the EDC system with source documents. All corrections or changes made to any study data must be appropriately tracked in an audit trail in the EDC system. An eCRF will be considered complete when all missing, incorrect, and/or inconsistent data have been accounted for.

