10.1.6 Data Validation

Validation checks programmed within the EDC system, as well as supplemental validation performed via review of the downloaded data, will be applied to the data in order to ensure accurate, consistent, and reliable data. Data identified as erroneous, or data that are missing, will be referred to the investigative site for resolution through data queries.

The eCRFs must be reviewed and electronically signed by the Investigator.

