3.6 Safety assessment

The Safety Population will be the primary population for the safety analyses. All safety endpoints will be summarized descriptively. No statistical inference will be applied to the safety endpoints.

AEs will be categorized by primary system organ class and preferred term as coded using the Medical Dictionary for Regulatory Activities (MedDRA) category designations. Summaries of AEs, including the number and percentage of patients who experience an AE, will be provided.

Laboratory values will be summarized descriptively, including the change from baseline. In addition, shift tables will be presented to describe the change in laboratory parameter values at post-baseline visits using normal range categories (low, normal, and high).

Vital signs will be summarized descriptively, including the change from baseline.

ECG results, as well as physical and neurological examination findings will be listed. Clinically relevant abnormal findings at baseline or during the study will be reported as baseline condition or AE, respectively.

4. Analysis timing

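### The SAP's rule for incomplete adverse event start dates ignores first dose, so an on-treatment event can be dated before Day 1 and lose treatment-emergent status

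*SAP*

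**What the plan says.** SAP 3.1.4 (Date Values) covers start and stop dates of AEs, concomitant medications and medical history. Its principle is that "the missing component(s) will be assumed as the most conservative value possible". Its concrete rule for start dates is that "if the start date is incomplete, the first day of the month will be imputed for the missing day and January will be imputed" when the month is missing; incomplete stop dates go to the latest day or month. On use, it says "Date imputation will only be used for computational purposes such as treatment-emergent status". Listings show dates as collected.

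The time origin is in SAP 3.1.1: "The day of the first dose of study drug will be Day 1". The SAP does not define treatment-emergent and gives no end to its window.

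The safety analysis in SAP 3.6 says "Summaries of AEs, including the number and percentage of patients who experience an AE, will be provided", without restricting this to treatment-emergent events; Protocol 9.1.2 reads the same way. Protocol section 8 says that AEs "will be monitored and documented from the time of first dose of study drug until the end of the study".

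**The concern.** For treatment emergence, the cautious error is to keep a doubtful event in. The rule takes the earliest date compatible with what is known and has no floor at first dose, so it pushes doubtful events out. On any definition that starts at first dose, two kinds of on-treatment AE lose the flag:

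- only the day is missing and onset was in the calendar month of first dose (unless first dose fell on the 1st);
- day and month are missing and onset was in the calendar year of first dose (unless first dose fell on 1 January).

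Safety and tolerability is a stated objective (SAP 2.1.2). With 10 to 15 patients, one patient is 1/15 = 6.7 to 1/10 = 10 percentage points of any incidence. If an output uses the flag, a single misdated event can be visible in it.

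**Working it through.** The documents give no figure on this point, so there is none to reproduce. The written rule can be applied to calendar dates.

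**Examples (non-leap year).** First dose 15 March, onset 20 March, day missing: imputed 1 March, which is Day -14. First dose 15 March, onset 20 June, day and month missing: imputed 1 January, which is Day -73.

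**Inputs.** Day 1 is first dose (SAP 3.1.1). Dosing runs over Days 1 to 168 (SAP 2.2.1). The follow-up call is nominally Day 198 (Protocol 6.1.6). Assumptions not in the documents: first dose is equally likely on each of 365 days, and onset is uniform over Days 1 to H, with H = 168 or 198. Denominators are 365 × 168 = 61,320 and 365 × 198 = 72,270.

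**Only the day missing.** In a month of L days there are L(L+1)/2 pairs of a first-dose day and an onset on or after it. The L pairs with first dose on the 1st are dated correctly, which leaves L(L-1)/2 misdated.

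- Misdated: 7 × 465 + 4 × 435 + 378 = 5,373.
- All onsets in the first-dose month: 7 × 496 + 4 × 465 + 406 = 5,738.

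**Day and month missing.** For first dose on day j of the year (j ≥ 2), misdated onsets number min(H, 366 - j).

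- H = 198: 167 × 198 + (197 × 198)/2 = 33,066 + 19,503 = 52,569.
- H = 168: 197 × 168 + (167 × 168)/2 = 33,096 + 14,028 = 47,124.

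| On-treatment AEs with a partial start date | Dated before first dose |
|---|---|
| Day missing, Days 1-198 | 5,373 / 72,270 = 7.4% |
| Day missing, Days 1-168 | 5,373 / 61,320 = 8.8% |
| Day missing, onset in first-dose month | 5,373 / 5,738 = 93.6% |
| Day and month missing, Days 1-198 | 52,569 / 72,270 = 72.7% |
| Day and month missing, Days 1-168 | 47,124 / 61,320 = 76.8% |

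The day-missing error falls early: over Days 1 to 28 the share is 52%. The day-and-month result depends on when patients start. First doses only in January to June give 99.2% (H = 198) and 99.4% (H = 168); only in July to December, 46.7% and 54.6%.

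**The other end of the window.** If the window closed at Day 168, onsets on Days 169 to 198 with only the day missing would be moved into it in 5,373 of 365 × 30 = 10,950 cases (49.1%). If it ran to the end of the study, this would not arise.

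**The case against.** The strongest objection is that no stated output changes. The planned summaries cover all AEs, the listings are not imputed, and the SAP mentions treatment emergence only as an example of a use. This stands, and it keeps the point minor.

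Partial dates should also be few. Protocol 10.1.1 says "An eCRF will be considered complete when all missing, incorrect, and/or inconsistent data have been accounted for", and Protocol 10.1.6 says "Data identified as erroneous, or data that are missing, will be referred to the investigative site for resolution through data queries". With site visits every six weeks, a missing month is unlikely. This stands too: the 73% to 77% figures apply to a rare kind of record, and the number of affected AEs could be zero.

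A third objection is that AEs are recorded only from first dose, so any event on the form is on-treatment. That follows from the text of Protocol section 8. However, the schedules in Protocol Appendix A and SAP Table 1 mark AEs at Screening, and the MRI text in Protocol section 8 lets Screening findings be recorded as AEs. Pre-dose events may therefore be in the data, and the flag is not redundant.

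Fourth, taking the earliest start and the latest stop gives the longest duration, which is a coherent sense of conservative, and the rule is introduced as an example. But it is the only operative instruction, and it gives the wrong direction for the one use that the SAP names.

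Finally, SAP section 6 defers detail to separate programming specifications, which were not available for this review. They may contain a floor at first dose. The SAP rule should still be right as written.

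**Conclusion.** The concern holds as a minor correction. The rule misclassifies on-treatment AEs for its own named purpose, and that conclusion needs no distributional assumption. The percentages do: they rest on uniform first-dose dates and onsets, and they are shares of AEs that already have a partial start date. The documents do not allow an expected number of affected events. Any effect is confined to output that uses the flag; the all-AE summaries and the listings are untouched. No bias in the safety results has been shown.

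**What to change.** In SAP 3.1.4, for AE start dates only, state:

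> If the known parts of the date are compatible with onset on or after first dose, impute the later of the first-dose date and the earliest date consistent with the known parts, unless the stop date (a partial stop date being taken as the latest date consistent with its known parts) precedes first dose. If the start date is wholly missing, impute the first-dose date under the same condition. Otherwise apply the current rule.

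Keep the current rule for medications (SAP 3.3.6) and medical history. Define treatment-emergent, including the end of its window, and say whether the SAP 3.6 summaries use it. The new rule leaves the 49.1% at Day 168 unchanged, so the end of the window has to be stated separately.

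Under this rule no on-treatment AE is dated before first dose. Its known parts are always compatible with onset on or after first dose, and its stop date, taken at its latest, is never before first dose.

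The cost is three sentences for the imputation rule, the definition, and a small program change. The downside is that some true pre-dose AEs would be flagged. Assume onsets uniform over the 8 weeks before first dose (365 × 56 = 20,440 pairs) and no usable stop date:

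- day missing: 5,373 / 20,440 = 26.3%;
- day and month missing: (0 + 1 + … + 55) + 309 × 56 = 1,540 + 17,304 = 18,844, or 92.2%.

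With a complete stop date 3, 7 or 14 days after onset, the day-missing share falls to 5.0%, 10.9% or 18.8%. This downside arises only if pre-dose events are recorded as AEs at all. It errs towards inclusion, which is the direction the SAP promises, and the listings still show the dates as collected.

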3.2 Analysis populations

3.2.1 Intent-To-Treat (ITT) population

The Intent-to-Treat (ITT) Population will include all patients who receive at least 1 dose of study drug.

3.2.2 Per-Protocol (PP) population

The Per-Protocol (PP) Population will include all patients who have a study drug compliance percentage of at least 80% over the entire study duration. The PP Population will be the primary population used for the PD and PK analyses, and for the analyses of the effects of objectrapib on cognition.

3.2.3 Safety population

The Safety Population will include all patients who receive at least 1 dose of study drug, same as the ITT population. The Safety Population will be the primary population used for the safety analyses.

3.3 Subject data and study conduct

3.3.1 Subject disposition

Subject disposition will be presented for all participants. Counts and percentages of participants who are included, complete the study, complete the treatment, prematurely discontinue from the study, reasons for study discontinuation, and primary reason for early termination was due to COVID-19 will be summarized by treatment and overall. For each scheduled visit, counts and percentages of participants who do not complete the visit, partially complete the visit in-person, or complete the visit virtually will be summarized. The denominator for calculating percentages will be based on the number of included participants.

Data listings for subject disposition and exclusion and inclusion criteria violations will be provided.

3.3.2 Protocol deviations

The Protocol Deviations will be identified as either CSR reportable or non-CSR reportable deviations. Counts and percentages of participants with CSR reportable protocol deviations by deviation category will be summarized for all participants. A listing of CSR-reportable protocol deviations will be generated.

CSR Reportable Deviations include:

- 1) Violations of Inclusion/Exclusion Criteria
- 2) Subject Met Withdraw Criteria and was Not Withdrawn
- 3) Subject Reviewed the Wrong Dose
- 4) Subject Took an Excluded Med or Had a Change to a Required Medication
- 5) Procedure Missed that Impacts Safety and/or Data Integrity
- 6) Violation of SAE/Safety Reporting Requirements

3.3.3 Analysis populations

Counts and percentages of participants in each analysis population will be summarized by treatment and in total based on all randomized participants. Reasons for exclusion from PP population will also be summarized.

3.3.4 Demographic and baseline characteristics

Demographic and Baseline characteristics including age, sex, education in years, APOE genotype, and cognition/function level (CDR global at baseline, MMSE at baseline, CFC at baseline) will be summarized for the ITT Population. If the variable is categorical, frequency and proportions will be mentioned. If normal distributed and numerical mean and SD will be shown. If non-normal numerical, median and IQR 25-75 will be shown. If they differ from the ITT Population, summaries will also be provided for the PP Population and the Safety Population.

3.3.5 Medical history

Counts and percentages of participants with medical history will be summarized based on ITT population.

3.3.6 Concomitant medications

Medication start and stop dates that are recorded on the CRF will be used to determine whether the medications are prior or concomitant to the study treatment. Concomitant medications are defined as those used on or after the first dose of study treatment. Prior medications are defined as those used prior to and stopped before the first dose of study treatment. The numbers and percentages of participants taking prior and concomitant medications will be summarized for the ITT population.

3.3.7 Study drug exposure and compliance

During every visit it is noted in the eCRF if the participant is compliant, with a 1 denoting the participant was compliant and a 0 denoting compliance was lower than 80%.

3.4 Efficacy assessment

The PP Population will be the primary population used for the PD and PK analyses, and for the analyses of the effects of obicetrapib on cognition. The drug compliance is noted after each visit. Drug compliance for overall study will be calculated with the mean of compliance of the variables noted below.

```
V3_drug_return_compliance_rate
V4_drug_return_compliance_rate
V5_drug_return_compliance_rate
V6_drug_return_compliance_rate
```

If at least 80%, participant will be included in the analysis.

3.4.1 Primary pharmacodynamic endpoints

Goal analysis: analyze change from baseline (V2; day 1) in levels of ApoA1, ApoE, and small HDL particles, in both CSF and plasma and ABCA1-driven cholesterol efflux in CSF at EOT (V6; day 168)

Variables:

- CSF and plasma ApoA1
- CSF and plasma ApoE
- CSF and plasma small HDL particles
- CSF ABCA1-driven cholesterol efflux

Methods: A Wilcoxon signed rank test will be used. We will be testing the difference between V2 (day 1; baseline) for plasma or V1 (Screening) for CSF and V6 (EOT; 168 days). Significant if p < 0.05. No multiple testing correction will be performed due to the highly correlative nature of the variables and explorative nature of the trial.

